An important component of SOLO is the testing of two different kinds of swabs, nylon-flocked and Dacron, for molecular and cytological adequacy and end user acceptability within a self-sampling and clinician-sampling context. We chose a nylon-flocked (NF) swab for use in SOLO given its high adequacy in our prior study: the Prevent Anal Cancer (PAC) Self-Swab Study (R01 CA215403, PI: [name]); however, this NF swab is unlikely to be available for clinical use in the future due to recent changes in the manufacturer's priorities. Since SOLO results need to be widely generalizable and relevant to anal cancer screening, we need to use a different NF swab model and assess its cytological and molecular performance characteristics in a pilot study before beginning SOLO. Given our prior success with a NF swab developed by Copan Italia s.p.a. (Brescia, Italy) we will test the feasibility of a new Copan swab developed for anal cancer screening.

We will test the cytological performance of the swab at two insertion depths, 3 cm and 5 cm, to determine which insertion depth is better at collecting cells from the squamocolumnar junction (SCJ), an anatomic site that is particularly vulnerable to carcinogenic transformation. We hypothesize that the 5 cm insertion will result in a higher quality specimen with cells from the SCJ. However, the deeper swab insertion may affect end user acceptability without increasing adequacy or quality.

We will test the new swab with 60 individuals who were participants in the PAC Self-Swab Study and who agreed be contacted for follow-up studies. Individuals will be randomized to use the new NF swab with either a 3 cm or 5 cm insertion depth. After consenting, individuals will receive written instructions and then conduct the self-sampling in private. Staff will take the swab in PreservCyt to the Medical College of Wisconsin Tissue Bank where it will be aliquoted for assessment of cytology and reflex HIV testing at Wisconsin Diagnostic Labs and HPV genotype at Moffitt Cancer Center. We have one objective: To ensure the use of a swab in SOLO that is comparable to the originally proposed swab for SOLO, determine the preliminary performance characteristics of the new NF swab. We have three hypotheses within the objective:

- **H1:** A higher proportion of the new NF swabs with 5 cm insertion will have SCJ cells compared to the NF swab for 3 cm insertion.

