5. Ability to understand a written informed consent document, and the willingness to sign it.
NOTE: this inclusion criterion is mandatory unless a waiver of the informed consent process and document is being requested.

C.2 Exclusion Criteria

A potential pilot study subject who meets any of the following exclusion criteria is ineligible to participate in the pilot study.

1. Presence of any contraindicating severe anal disease or condition, e.g., anal stenosis.

D Pilot Study Accrual Goals and Study Duration

A total of 60 SGM will be recruited from the greater Milwaukee metropolitan area. Accrual will last for approximately 2 months.

The pilot study will reach pilot study completion within 4 months of the beginning of accrual.

E Subject Recruitment and Registration

E.1 Recruitment

Potential SGM participants will be recruited first from the group of individuals who consented into the PAC Self-Swab Study (PRO00032999) and then indicated an interest in a follow-up study (n=126). We will enroll those aged \geq 35 years. Persons reporting no sex with men during the last five years will be included if they identify as an SGM individual.

If the initial recruitment results in fewer than 60 people, we will recruit by other means:

1. Advertising on geo-located social/dating apps commonly used by older SGM, e.g., Scruff, Growlr, and Jack'd. We will run advertisements on the apps using a 25-mile radius from the city center in Milwaukee to reach people throughout the city's metro area.
2. The use of print materials in gay-friendly business and a website (mindyourbehind.org) used in the PAC Self-Swab Study. The material will mention the study is recruiting for an anal cancer screening study.

Recruitment material will be approved by an MCW Institutional Review Board (IRB). The SOLO Study Coordinator in Milwaukee will oversee recruitment activity. We will record recruitment activities.

E.2 Consenting

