Potential participants will be screened using an online computer-assisted self-interview (CASI). Those who are eligible will be asked to leave contact information. Study staff will contact eligible individuals, provide an overview of the pilot study, and invite the individual to a schedule a consenting session which will be followed by the cytology screening at the Curative Building on the MCW campus. Those who are not eligible will be thanked for their interest and provided links to vetted anal cancer education websites. Minimal Protected Health Information (PHI) will be collected in the eligibility survey.

At the consenting session staff will first ask the eligible individual to confirm their email address, name, and birthdate. The session will occur in a closed office and include information about 1) high rates of anal cancer in SGM, 2) anal cancer screening and the role of swabbing, 3) pilot study activities, and 4) the potential harms and benefits of participation. The staff member obtaining consent will emphasize that participation is voluntary and that participants can choose to join and,

if desired, leave the pilot study at any point without any repercussions. The ICF will also notify individuals that we will collect their street address to support payment using the MCW visa card.

Prior to obtaining their signature, the staff member will ask the individual if they have any questions and, if not, to briefly review their understanding of their participation by asking simple questions about the pilot study to be sure the information was clearly understood.

Individuals agreeing to provide consent will sign an ICF hard copy. It will be photocopied with the copy given to the participant.

F Pilot Study Design and Intervention

F.1 Study Design

This pilot feasibility study will use a randomized controlled trial design.

Figure 1 illustrates the pilot study design.

F.2 Randomization

Consented individuals will be randomized to either the intervention (5 cm insertion depth) or the control (3 cm insertion depth) arm using a number generator in REDCap. If the number is .0000 to .4999, the individual will be assigned to the intervention condition. If the number is .5000 to .9999, the individual will be assigned to the control condition.

The participant is considered enrolled in the pilot study when they sign a consent form and are randomized to either the intervention or control arm.

F.3 Cytology Sampling

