1. A comparison of the proportions of individuals who collect squamocolumnar cells when using a NF swab with a 5 cm vs. a 3 cm insertion depth.
2. A comparison of the proportions of individuals who collect cytologically adequate specimens when using a NF swab with a 5 cm vs. a 3 cm insertion depth.
3. A comparison of the proportions of individuals who collect adequate specimens for molecular genotyping when using the new NF swab vs. the original swab used in the PAC Self-Swab Study.
4. A comparison of the acceptability and pain performance of the new NF swab vs. the original swab.

H.2 Power for Endpoints

This pilot feasibility study does not have the power to make conclusive statements about the study endpoints.

H.3 Analysis Plan

H.3.1 Preliminary analyses

We will assess the success of randomization. For surveys, we will calculate item response rates for each arm of the study and for subgroups based on HIV status, race/ethnicity, and education.⁴³

After evaluating missing survey data, we will use multiple imputation⁴⁴ to maintain the maximum sample size if data are missing at random. Sensitivity analyses will compare results if data are not missing at random.⁴⁵

In each study arm, we will analyze frequencies of survey items, demographics, other domains, adverse events, and serious adverse events.

H.3.2 Primary Endpoint 1

The presence of cells from the squamocolumnar junction will be assessed in each specimen (Yes/No). Proportions of specimens with squamocolumnar cells will be compared for the 5 cm and 3 cm swabs.

H.3.3 Primary Endpoint 2

Cytologic adequacy is defined as the presence of ~2000-3000 nucleated squamous cells. Proportions of adequate specimens will be compared for the 5 cm and 3 cm swabs.

H.3.4 Primary Endpoint 3

The PAC Self-Swab Study molecular adequacy estimates, given study size, were quite precise with narrow confidence limits. The estimates derived from this pilot study will have wider confidence limits. The original and new swabs will be considered to have commensurate molecular adequacy if the exact confidence limits of the original PAC Self-Swab Study swab are covered by the exact confidence limits of the piloted swab.

H.3.5 Primary Endpoint 4

Each participant will receive a short cytology CASI immediately after the cytology screening to rate their acceptability of the cytology screening on a Likert scale and pain on a visual scale.³⁷ Proportions of individuals' ratings for adequacy and pain will be compared for

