- 1) the 5 cm and 3 cm swabs, and
- 2) the new NF swab vs the original swab.

The Exact 95% confidence limits surrounding proportions for acceptability and pain will be compared for overlap for 5 cm vs 3 cm insertion depths.

The comparison of acceptability/pain between the new NF swab and the original swab will be analyzed as in H.3.4.

I ADVERSE EVENTS AND OTHER REPORTABLE INCIDENTS

This study is low risk to participants due to its design and the nature of the intervention being tested (i.e., cancer screening and behavioral interventions). No investigational drugs or devices are involved.

Even though this study does not test a therapeutic intervention, this study will follow the Cancer Therapy Evaluation Program (CTEP) guidelines for reporting of adverse events. All expedited adverse event reports are required to be submitted to the MCW Institutional Review Board (IRB).

I.1 Definitions

I.1.1 Adverse Event (AE)

Any untoward medical occurrence in an individual or clinical investigation subject administered an interventional product and which does not necessarily have to have a causal relationship with this intervention.

This study will utilize the NCI Common Terminology Criteria for Adverse Events (CTCAE) version 5.0, located on the CTEP web site:

https://ctep.cancer.gov/protocolDevelopment/electronic_applications/ctc.htm

AEs may be spontaneously reported by the subject and/or in response to an open question from study personnel or revealed by observation, physical examination or other diagnostic procedures.

I.1.2 Serious Adverse Event (SAE)

Serious Adverse Event (SAE) means any untoward medical occurrence that results in any of the following outcomes:

- **Death.** Results in death.
- **Life-threatening.** Is life-threatening (refers to an AE in which the participant was at risk of death at the time of the event. It does not refer to an event which hypothetically might have caused death if it were more severe).
- **Hospitalization.** Requires inpatient hospitalization ≥ 24 hours or prolongation of an existing hospitalization.
- **Disability/incapacity.** Results in persistent or significant disability or incapacity. (Disability is defined as a substantial disruption of a person's ability to conduct normal life functions).
- **Pregnancy**

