questions) is reasonable within the context of important educational and personal health information gained by the participant. The knowledge gained by this research will benefit science by determining the utility of a 3 cm or 5 cm swab for use in the parent SOLO study. If SOLO finds that self-sampling supports clinic attendance, that will benefit the performance of anal cancer screening procedures in society. For these reasons, the potential benefits of the pilot study are reasonable in relation to the anticipated benefits to the pilot study participants.

K.6 Protection of Human Subjects

K.6.1 Protection from Unnecessary Harm

MCW is responsible for protecting all individuals involved in human experimentation. This is accomplished through the IRB mechanism and the informed consent process. The IRB reviews all proposed studies involving human experimentation and ensures that the subject's rights and welfare are protected and that the potential benefits and/or the importance of the knowledge to be gained outweigh the risks to the individual. The IRB also reviews the informed consent document associated with each study to ensure that the consent document accurately and clearly communicates the nature of the research to be done and its associated risks and benefits.

K.6.2 Protection of Privacy

To ensure confidentiality, each participant is assigned an anonymous study ID, which is then used on all pilot study forms that collect participant data. Study IDs are linked to participant names and other private identifiable information in only one location, on an encrypted, firewall-protected, electronic document housed on MCW's server. All study forms are kept on the MCW server or HIPAA-compliant MCW data-sharing platform and access is restricted to authorized study personnel.

K.6.3 Protection Against Additional Risks

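### The comparisons with the original swab appear to combine both insertion depths, so a commensurate result can hide one depth that falls short

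*Combined protocol and SAP*

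**What the plan says.** Section A states that "Individuals will be randomized to use the new NF swab with either a 3 cm or 5 cm insertion depth", and Section D sets the total at 60. Randomization in F.2 is simple, with probability one half for each arm: "If the number is .0000 to .4999, the individual will be assigned to the intervention condition".

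Endpoint 3 in H.1 compares the proportions who collect "adequate specimens for molecular genotyping when using the new NF swab vs. the original swab used in the PAC Self-Swab Study"; depth is not mentioned. H.3.4 then makes a yes/no call: the swabs are treated as commensurate if "the exact confidence limits of the original PAC Self-Swab Study swab are covered by the exact confidence limits of the piloted swab". For endpoint 4, H.3.5 lists the 5 cm versus 3 cm comparison and the new-versus-original comparison as separate items. The first is judged by overlap of exact 95% limits. For the second: "The comparison of acceptability/pain between the new NF swab and the original swab will be analyzed as in H.3.4".

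On how the result will be used, K.5.2 describes the scientific gain as "determining the utility of a 3 cm or 5 cm swab for use in the parent SOLO study".

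**The concern.** H.3.4 and the second item in H.3.5 set one new swab, with one set of limits, against the original. Both list or treat this separately from the depth comparison, so the text most naturally describes all 60 participants as a single group. SOLO, however, is expected to take forward a particular depth. A combined estimate describes a roughly even mixture of depths, and a good result at one depth can offset a poor one at the other.

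The stated objective (B.1) is to ensure that SOLO uses a swab comparable to the original. If the depth carried forward is the weaker one, a combined commensurate result would not show that this objective had been met for it. Endpoint 3 is the most exposed, because H.3 plans no comparison of molecular adequacy between 5 cm and 3 cm.

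**Working it through.** The plan has no power, margin or sample-size figure for this comparison, so there is nothing to reproduce. The check applies the H.3.4 rule to the combined group and to one depth.

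**Inputs**
- From the documents: 60 participants (Section D), an expected 30 per depth (F.2), and the coverage rule (H.3.4). Simple randomization gives exactly 30/30 with probability 0.10; the 95% range for one arm is 22 to 38.
- Assumed: a 95% level for H.3.4, taken from H.3.5, and the PAC counts, which the documents do not give.

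**Formulas**
- Exact (Clopper-Pearson) limits for x of n: lower = Beta quantile 0.025 with parameters (x, n−x+1); upper = Beta quantile 0.975 with parameters (x+1, n−x), or 1 if x = n.
- A group passes if its lower limit is at or below PAC's lower limit and its upper limit is at or above PAC's upper limit.
- P(masking) = sum over a, b of Bin(a; 30, p3) × Bin(b; 30, p5), taken over outcomes where a+b of 60 passes and b of 30 has an upper limit below PAC's upper limit.

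**1. A single outcome.** Take PAC as 190/200, limits 91.0–97.6%.
- Combined: 30/30 + 26/30 = 56/60, limits 83.8–98.2%. These cover PAC, so the group passes.
- Weaker depth alone: 26/30, limits 69.3–96.2%. The upper limit is below 97.6%, so it fails.
- Point differences from PAC: 93.3 − 95.0 = −1.7 points combined, but 86.7 − 95.0 = −8.3 points for the weaker depth.

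**2. How often.** Take PAC as 90%. At 180/200 its limits are 85.0–93.8%; the combined group passes with 52–56 of 60 and one depth with 25–29 of 30.

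| PAC n | True rates | Combined passes | Weaker depth passes | Combined passes, weaker fails |
|---|---|---|---|---|
| 200 | 97% / 75% | 0.51 | 0.20 | 0.33 |
| 200 | 95% / 75% | 0.43 | 0.20 | 0.24 |
| 400 | 95% / 75% | 0.59 | 0.20 | 0.39 |
| 200 | 90% / 80% | 0.43 | 0.43 | 0.11 |
| 200 | 90% / 90% | 0.72 | 0.88 | 0.02 |
| 200 | 80% / 80% | 0.13 | 0.43 | 0.01 |

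In the rows with equal rates, the last two columns refer to one given depth.

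**3. Where it disappears.** With PAC at 98% and n from 120 to 1000, at most one pair of outcomes (weaker depth with 30/30 at the other) passes combined while the weaker depth fails. At n = 200 that pair is 28/30 with 30/30.

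**4. The endpoint 4 overlap check.** 23/30 (57.7–90.1%) and 30/30 (88.4–100%) still overlap. With true rates of 97% and 75%, the intervals separate in only about 28% of trials.

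**5. The same rule within each arm.** Fewer participants give wider limits, which cover PAC more easily. With PAC at 180/200 and both depths truly 80%, the pass probability is 0.13 combined and 0.43 per arm. With PAC at 190/200 and both depths truly 85%, it is 0.04 and 0.32.

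**The case against.** The case for the plan as written has four parts.

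- **Pooling is implied, not stated.** Neither H.3.4 nor H.3.5 says that the depths are combined. This stands: the defect is an unstated analysis group together with the absence of any by-depth comparison with PAC.
- **The plan does not predict a depth effect on these endpoints.** A reader might infer one from Section A, which says "the deeper swab insertion may affect end user acceptability without increasing adequacy or quality". That is a possibility, not an expectation. H4 expects similar acceptability and pain at both depths, H1 and H2 concern cytology, and nothing predicts that depth changes molecular adequacy. Combining the depths to answer a question about the swab model is consistent with these hypotheses.
- **Acceptability and pain will be visible by arm.** H.3.1 tabulates survey items in each arm, and H.3.5 compares the depths. This stands as visibility, but the frequencies do not feed the commensurate decision and the overlap check is weak. Neither helps endpoint 3.
- **The combined analysis is the stricter one when the new swab is inferior at both depths.** This stands (step 5). A reader might infer that the combined estimate should be replaced or demoted; the figures do not support that.

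A reader might also infer that swab model and depth are confounded in the comparison with PAC. That cannot be judged, because the PAC insertion depth is not given. Finally, H.2 disclaims conclusive statements, so it would be too strong to say that the pilot certifies a failing depth. H.3.4 nevertheless makes a yes/no call, so the disclaimer does not remove the point.

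**Conclusion.** The point holds as a cheap improvement to the plan. On its natural reading, the comparison with PAC uses both depths combined and offers no depth-specific answer, although SOLO's choice is between depths. It is clearest for molecular adequacy and weaker for acceptability and pain, where arm-level results will be seen.

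The size depends on PAC figures that the documents do not give. With PAC assumed at 90%, masking occurs in roughly 24% to 39% of trials when the true rates differ by 20 to 22 points. It falls to about 11% for a 10-point difference and to 1–2% when the depths are alike. If PAC adequacy is about 98%, there is almost no room for it. All figures assume 30 per depth and 95% limits.

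**What to change.** 1. State in H.3.4, and for the second comparison in H.3.5, that the group compared with PAC is both depths combined, if that is what is meant.
2. For endpoints 3 and 4, also report each depth's proportion and its difference from PAC with a 95% CI, alongside the combined estimate.
3. Add a 5 cm versus 3 cm comparison of molecular adequacy.
4. State the insertion depth used in PAC, so that the reader can see which arm, if either, is like for like.
5. Word the comparability conclusion for the depth carried into SOLO, using that depth's own estimate and CI.
6. Do not apply the H.3.4 coverage rule separately within each arm. Any yes/no criterion by depth should be one that imprecision cannot satisfy, such as a margin set in advance.

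The cost is some analysis-plan wording and a few table rows, with no new participants or procedures. The downside is wider per-arm intervals: at 90%, 73.5–97.9% with 27/30 against 79.5–96.2% with 54/60.

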- **H2:** A higher proportion of the new NF swabs with 5 cm insertion will be adequate for cytopathology interpretation compared to the NF swab for 3 cm insertion.
- **H3:** The new NF swab will have molecular adequacy that is commensurate with the original NF swab used in the PAC Self-Swab Study.
- **H4:** The new NF swab will have acceptability/pain performance commensurate with the originally proposed NF swab and the 5 cm insertion depth will have similar acceptability/pain performance as the 3 cm insertion depth.

Our expected outcomes are cytological and molecular preliminary performance characteristics of the new NF swab in addition to user acceptability. These outcomes will help ensure the use of a viable swab in SOLO that is relevant in future anal cancer screening programs.

B Pilot Study Objective and Endpoints

B.1 Pilot Study Objective

To ensure the use of a swab in SOLO that is comparable to the originally proposed swab for SOLO, determine the preliminary performance characteristics of the new NF swab.

B.2 Pilot Study Endpoints

1. A comparison of the proportions of individuals who collect squamocolumnar cells when using a NF swab with a 5 cm vs. a 3 cm insertion depth.
2. A comparison of the proportions of individuals who collect cytologically adequate specimens when using a NF swab with a 5 cm vs. a 3 cm insertion depth.
3. A comparison of the proportions of individuals who collect adequate specimens for molecular genotyping when using the new NF swab vs. the original swab used in the PAC Self-Swab Study.
4. A comparison of the acceptability and pain performance of the new NF swab vs. the original swab and the 5 cm and 3 cm insertion depth.

C Pilot Study Eligibility

The pilot study team will evaluate eligibility according to the following criteria. Individuals must meet all inclusion and none of the exclusion criteria to be registered on to the pilot study. Any questions or concerns regarding eligibility should be directed to the PI, [name] ([contact]).

C.1 Inclusion Criteria

A potential pilot study subject who meets all of the following inclusion criteria is eligible to participate in the pilot study. Note that these criteria apply regardless of HPV vaccination status or disability status.

1. Aged \geq 35 years.
2. Must be either:
 - a) A cisgender or transgender sexual minority man, or
 - b) A transgender woman who has sex with men.
3. Resides in the Milwaukee metropolitan area.
4. Speak and understand English.

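### The rule for calling the new swab commensurate with the original can fail a better swab and passes a worse one more easily as precision falls

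*Combined protocol and SAP*

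**What the plan says.** Hypothesis H3 in section A is that "The new NF swab will have molecular adequacy that is commensurate with the original NF swab". Section H.3.4 turns this into a rule: the swabs count as commensurate if the "exact confidence limits of the original PAC Self-Swab Study swab are covered by the exact confidence limits of the piloted swab". The same paragraph describes the original study's estimates as precise and adds: "The estimates derived from this pilot study will have wider confidence limits". It gives no margin, direction, confidence level or numerical limits for the original swab, and does not say whether the 5 cm and 3 cm arms are pooled.

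H.3.5 extends the rule: "The comparison of acceptability/pain between the new NF swab and the original swab will be analyzed as in H.3.4".

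On use, section A says of the cytological, molecular and acceptability results: "These outcomes will help ensure the use of a viable swab in SOLO". H.2 says the pilot "does not have the power to make conclusive statements about the study endpoints".

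**The concern.** Coverage requires two things at once: the pilot's lower limit must be at or below the original's lower limit, and the pilot's upper limit must be at or above the original's upper limit. Two consequences follow.

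- A very good pilot result raises its own lower limit. Once that exceeds the original's lower limit, the rule withholds the commensurate label because the new swab did too well.
- A wide pilot interval covers a narrow one more easily, so weak data favour passing. Evidence of similarity normally requires the interval to lie inside a stated margin; here the pilot interval has to be wide enough to contain the other one.

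The label answers the stated objective, comparability with the original swab, so it can mislead in both directions. For pain, a clearly less painful swab can fail for the same reason.

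**Working it through.** **Inputs.** Pilot size is 60 (section D). Simple randomization gives about 30 per arm (F.2). Two-sided 95% exact limits are assumed: H.3.5 states 95%, H.3.4 states no level. The original (PAC) counts are not in the documents, so every PAC result below is an assumption. The plan has no figure of its own to reproduce here.

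**Exact limits.** For x adequate specimens out of n, the lower limit is the 0.025 quantile of Beta(x, n−x+1) and the upper limit is the 0.975 quantile of Beta(x+1, n−x). When x = n, the lower limit is 0.025^(1/n): 0.9404 for n=60 and 0.8843 for n=30. Other pooled results: 59/60 gives 91.06–99.96%, 58/60 gives 88.47–99.59%, 56/60 gives 83.80–98.15%.

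**When a result can be too good.** No count has a higher lower limit than 60/60, so this failure is possible at n=60 only if the original's lower limit is below 94.04%.

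| Assumed PAC result | Exact 95% limits | Pilot counts of 60 that pass |
|---|---|---|
| 123/126 (97.6%) | 93.20–99.51% | 58–59 |
| 194/200 (97.0%) | 93.58–98.89% | 57–59 |
| 232/240 (96.7%) | 93.54–98.55% | 57–59 |
| 196/200 (98.0%) | 94.96–99.45% | 58–60 |
| 235/240 (97.9%) | 95.21–99.32% | 58–60 |
| 190/200 (95.0%) | 91.00–97.58% | 56–58 |
| 216/240 (90.0%) | 85.49–93.49% | 52–56 |

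**Probability of passing.** This is the binomial probability summed over the passing counts, n=60.

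| True adequacy of new swab | PAC 190/200 | PAC 216/240 |
|---|---|---|
| Identical | 63% | 72% |
| 5 points better | 0% (perfect swab) | 35% |
| 99% | 12% | 0.3% |
| 5 points worse | 26% | 43% |
| 10 points worse | 4% | 13% |

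At 216/240 a swab 5 points worse passes more often than one 5 points better. Differences from 216/240 (Newcombe intervals, independent samples assumed): 52/60 passes with a difference of −3.3 points (95% CI −14.6 to +4.5); 60/60 fails with +10.0 points (+3.2 to +14.4).

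**Effect of precision.** With PAC 190/200 and true adequacy of 85%, the pass probability is 40.5% at n=20, 32.2% at n=30, 4.2% at n=60 and 0.2% at n=120. An identical swab also passes less often with more data: 93.9% at n=30, 62.8% at n=60, 46.9% at n=120. The trend is strong but not strictly monotone, because counts are discrete: with PAC 116/120 and a swab 5 points worse, it is 49.5% at n=20, 53.8% at n=30 and 10.9% at n=60.

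**Effect of pooling.** Per arm (n=30) with PAC 190/200, 27 to 30 pass, so a perfect arm passes, but a swab 10 points worse passes 32% of the time instead of 4%. With PAC 216/240, 30/30 still fails, and 10 points worse passes 43% instead of 13%.

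**Pain.** Suppose pain is dichotomized and the original rate was 48/240 (20%, exact limits 15.1–25.6%). Then 9 to 15 of 60 pass. An identical swab passes 74% of the time, one that halves pain to 10% passes 14%, and one that raises it to 30% passes 24%.

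**The case against.** The failure of a better swab depends on a figure the documents do not give. Section A says the original swab was chosen "given its high adequacy in our prior study", and H.3.4 describes its limits as narrow; both fit a lower limit of 94.0% or more, in which case nothing fails at n=60 for being too good. That stands, and this half of the point is conditional. It does not remove the other half: at 196/200, a swab 10 points worse still passes 2% of the time at n=60 and 11% at n=30. Observed adequacy of 96.7% to 97.6% is also high, and there 60/60 fails.

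Commensurate could mean similar in both directions, so that excluding a clearly better swab is intended. Such a reading would still need a margin on each side, and the present rule has none and still rewards imprecision.

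Pooling is the natural reading, since Endpoint 3 names the new swab and no depth. That is fair; the n=30 figures show what the alternative reading would do. The pain figures are illustration only: H.3.5 uses a visual scale and gives no cut-off.

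Finally, H.2 disclaims power, no go/no-go decision hangs on the label, and both intervals will be visible to the team. This limits the consequence, but it does not make a pre-specified label point the right way.

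**Conclusion.** The point holds. That the containment rule can penalize a better result and reward imprecision follows from its wording. The 94.0% threshold is exact for n=60 and two-sided 95% limits. Whether a better swab would in fact be failed on adequacy depends on the original study's lower limit, which the sponsor holds and can check at once. The pass probabilities are conditional on assumed PAC counts; those at 216/240 and for pain illustrate the mechanism and do not predict what will happen. The result is a possibly wrong label in an unpowered pilot, not a failed trial. It should be fixed before the data are examined.

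**What to change.** In H.3.4 and the new-versus-original part of H.3.5:

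1. Replace containment with a one-sided criterion fixed before data are seen: commensurate if the new swab's lower exact 95% limit is not below the PAC estimate minus a sponsor-chosen margin. For pain, use the mirror image on the upper limit, with the cut-off defined.
2. State that the two depth arms are pooled and that limits are 95%.
3. Report the new-minus-original difference with a 95% confidence interval reflecting uncertainty in both estimates and any participant overlap. Overlap is likely, because E.1 says: "Potential SGM participants will be recruited first from the group of individuals who consented into the PAC Self-Swab Study".
4. Call any other result inconclusive, not a failure to be commensurate.

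The margin should be chosen from its operating characteristics. Examples at n=60, proposed rule versus current rule:

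| Case | Passing counts | Identical | Better swab | Worse swab |
|---|---|---|---|---|
| PAC 190/200, 10 points | 57–60 | 65% vs 63% | 99% adequacy: 99.7% vs 12% | 10 points worse: 1.5% vs 4% |
| PAC 216/240, 15 points | 52–60 | 86% vs 72% | 99% adequacy: 100% vs 0.3% | 10 points worse: 13% vs 13% |
| Pain 48/240, 15 points | 0–13 | 69% vs 74% | Pain halved: 99.8% vs 14% | Pain 30%: 10% vs 24% |

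**Cost.** The change needs wording and a margin, with no extra participants or procedures. The documents give no source for a margin.

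- A tight margin can pass an identical swab less often. At 10 points this is 65% vs 77% for PAC 228/240, 74.5% vs 90.2% for 233/240, 44% vs 72% for 216/240, and 32% vs 74% for pain at 48/240.
- A loose margin can admit a worse swab more often. At 15 points, a swab 10 points worse passes 10% vs 4% for PAC 228/240 and 14% vs 2% for 196/200; one 5 points worse passes 44% vs 26% for 190/200.
- At PAC 196/200 or 235/240, the 10-point rule accepts exactly the same results as the current one.
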